**REVISION HISTORY**

Revision #	Version Date	Summary of Changes	Consent Change?
1	8/17/21	Requested modifications to consent and protocol as detailed in the response letter.	Yes
2	9/23/21	Added study personnel; added 2 additional measures; revised TIP intervention script.	No

PROTOCOL TITLE: Development and Evaluation of a Tonic Immobility Focused Psychoeducational Intervention - RCT

## 1.0 Study Summary

Study Title	Development and Evaluation of a Tonic Immobility Focused Psychoeducational Intervention - RCT
Study Design	Randomized Controlled Trial
Primary Objective	To evaluate the efficacy of a brief-web-based intervention (Tonic Immobility Psychoeducation; TIP) intended to educate about tonic immobility (TI) within a sample of those who experienced TI in the context of a traumatic event.
Secondary Objective(s)	(1) TIP will significantly reduce feelings of posttraumatic feelings of guilt and shame compared to control (2) TIP will significantly reduce PTSD symptoms across time relative to control (3) Reduction in trauma-related guilt and shame will mediate the association between condition and changed in PTSD symptoms at follow-up.
Research Intervention(s)/Investigational Agent(s)	Tonic Immobility Psychoeducation Health Education Training
IND/IDE #	
Study Population	Adults who endorse prior TI during a traumatic event and elevated PTSD symptoms
Sample Size	120
Study Duration for individual participants	1 month
Study Specific Abbreviations/Definitions	TI = Tonic Immobility TIP = Tonic Immobility Psychoeducation HET = Health Education Training PTSD = Posttraumatic Stress Disorder

PROTOCOL TITLE: Development and Evaluation of a Tonic Immobility Focused Psychoeducational Intervention - RCT

## 2.0 Objectives\*

- 2.1 A randomized controlled trial is planned to evaluate a brief, web-based intervention intended to educate about tonic immobility (TI) within a sample of those who experienced TI in the context of a traumatic event.
- 2.2 It is hypothesized that the TIP intervention will show benefits in a sample of those who have experienced a traumatic event. Specifically, we hypothesize that: TIP will significantly reduce feelings of posttraumatic feelings of guilt and shame compared to control; TIP will significantly reduce PTSD symptoms across time relative to control; reduction in trauma-related guilt and shame will mediate the association between condition and changed in PTSD symptoms at follow-up.

## 3.0 Background\*

- 3.1 Tonic Immobility (TI) is a common defensive response in situations involving extreme fear such as physical and sexual assault, and its occurrence is influenced by both situational and individual difference factors. Previous research has estimated the prevalence of TI among sexual assault survivors to be between 37 to 70% (Fusé et al., 2007; Galliano et al., 1993; Heidt et al., 2005; Möller et al., 2017). Additional research among urban violence victims and anecdotal reports from combat veterans suggest similar experiences among these groups (Gallup & Rager, 1996; Solomon & Mukulincer, 2006; Fiszman et al., 2008). Although TI is adaptive in certain circumstances, it has been shown to contribute to increases in negative emotion, particularly guilt and shame, along with posttraumatic stress disorder (PTSD) symptoms. Moreover, several studies have demonstrated an association between TI and poorer recovery from PTSD (Fiszman et al., 2007; Lima et al., 2010; Hagenaaars & Hagenaaars, 2020).
- 3.2 Among other cognitive-behavioral techniques, experts in the field of posttraumatic stress emphasize the importance of psychoeducation about common reactions during and after trauma exposure (Foa & Rothbaum, 2001; Herbert & Sageman, 2004; Resick et al., 2017). However, neither brief psychoeducational interventions nor the current frontline treatments for PTSD, have focused significant attention on the experience of TI (Foa et al., 2007; Resick et al., 2017). Thus, the interpretation of TI during a traumatic event and the potentially detrimental changes in cognition, emotion, and behavior that result from it, are not directly addressed in any of the current empirically informed intervention protocols. Therefore, the current study aims to evaluate the effects of a brief TI-focused psychoeducation intervention on negative emotions, cognitions, and PTSD symptoms.

**PROTOCOL TITLE: Development and Evaluation of a Tonic Immobility Focused Psychoeducational Intervention - RCT**

3.3 The framework of this intervention was modeled after psychoeducation paradigms used in previous research and found to be effective (e.g. anxiety sensitivity focused psychoeducation intervention; Schmidt et al., 2014).

**4.0 Study Endpoints\***

- 4.1 Recruitment will stop after enrolling 120 participants. Data collection will continue until all enrolled participants have completed their Month 1 follow-up appointment, at which point data will be prepared for analysis
- 4.2 This is a minimal risk study. There are no safety endpoints given that there are no safety risks associated with the study.

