6.3 The risks to human subjects in the proposed study are minimal. Nevertheless, precautions will be taken to minimize participants' risk in the proposed study. All individuals will be informed of the nature of the investigation and the types of assessments and procedures. Participants will be asked to fill out an informed consent statement prior to participating in the project. Should a participant experience emotional distress including strong emotional or physical reactions to the intervention, a graduate-level therapist supervised by [name] will be called in to meet with the participant. Therapists will assist the participant in implementing coping skills to tolerate and reduce distress (e.g., deep breathing, self-soothing). [name] or an alternate clinical supervisor with the FSU Psychology Clinic will be on call for consultation as needed at all times.

PROTOCOL TITLE: Development and Evaluation of a Tonic Immobility Focused Psychoeducational Intervention - RCT

**6.4 Safeguards for Protecting Against COVID-19.** To reduce risk of COVID-19, our study team plans to follow standard COVID-19 precautions such as social distancing, mask wearing, and the sanitization of surfaces. However, participants will be informed that the voluntary disclosure of their full COVID-19 vaccination status is an alternative to COVID-19 related precautions, and they would be able to remove their masks during the baseline appointment. Staff will make a note in the study log of who has shown full COVID-19 vaccination documentation. The dialogue below will be said to participants when telling them about vaccination procedures:

- *"In order to protect against COVID-19 or Coronavirus, if you come to the lab we will follow certain precautions including social distancing and use of masks. However, we don't have to do this for persons who have completed a full COVID-19 vaccination. You may, if you'd like, share with us information about your COVID-19 vaccination, but this is your decision and is not required. You can still come to the lab and we will follow our usual COVID-19 precautions."*

**6.5** The following self-report measures will be used throughout the study.

**Demographic survey.** A self-report questionnaire will be used to assess participant demographic information. Specifically, various demographic variables will be assessed including gender, ethnicity, race, sexual orientation, and educational/occupational level.

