## **14.0 Withdrawal of Subjects\***

*14.1 Describe anticipated circumstances under which subjects will be withdrawn from the research without their consent.*

Possible reasons for removal include failure to complete the TIP intervention or self-report measures.

*14.2 Describe procedures that will be followed when subjects withdraw from the research, including partial withdrawal from procedures with continued data collection.*

The participant will be told they can leave the research at any time and it will not be held against them. All data collected prior to withdrawal will be securely stored and analyzed unless otherwise requested. Participants will be able to contact the PI to request the removal of their data, if so desired.

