### Self-report measures

It is unlikely that participants will be at risk for emotional or physical harm as a result of study participation. However, there is a slight possibility that participants may experience emotional discomfort or distress while completing study tasks. Based upon our past research, any distress reactions due to completion of questionnaires is typically acute (i.e., few minutes in duration) and relatively minor.

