### Interventions

HET has been used in prior research studies with no adverse effects. Content is related to healthy living and stress management, and not expected to cause distress.

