## PROTOCOL TITLE: Development and Evaluation of a Tonic Immobility Focused Psychoeducational Intervention - RCT

TIP has been modeled after a previous intervention which has been used in several studies and has a high level of acceptability as well as gold-standard evidence-based treatments for trauma. Although the information presented in the training should be no more anxiety-provoking than situations experienced in day-to-day life, it is possible that some participants may have strong emotional or physical reactions to information covered in the intervention. However, we believe prolonged distress is unlikely and feel that most participants will derive benefit from the interventions.

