## 18.0 Provisions to Monitor the Data to Ensure the Safety of Subjects\*

*This section is required when research involves more than Minimal Risk to subjects.*

N/A

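### Section 4.2 sets no safety endpoints on a premise that sections 6.3 and 15.1 contradict, so acute reactions to TIP and individual worsening would not be counted by arm

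*Combined protocol and SAP*

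**What the plan says.** The protocol (which contains the analysis plan in section 17.1) addresses harm in several places.

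- Section 4.2 calls the study minimal risk and then adds: "There are no safety endpoints given that there are no safety risks associated with the study".
- Section 15.1, on self-report measures: "there is a slight possibility that participants may experience emotional discomfort or distress while completing study tasks". This applies to both arms.
- Section 15.1, on the control: "HET has been used in prior research studies with no adverse effects". Its content is not expected to upset participants.
- Section 15.1, on TIP: "it is possible that some participants may have strong emotional or physical reactions to information covered in the intervention". The same paragraph compares the content to everyday stress and considers lasting distress improbable.
- Section 6.3 provides for a response: "Should a participant experience emotional distress including strong emotional or physical reactions to the intervention, a graduate-level therapist" is called in, with a supervisor on call. Section 15.1 repeats the arrangement.
- Section 14.1, on removal without consent: "Possible reasons for removal include failure to complete the TIP intervention or self-report measures". HET is not named.
- Section 18.0 is answered N/A, under the template note "This section is required when research involves more than Minimal Risk to subjects".
- Section 17.1 compares the arms on guilt, shame and PTSD symptoms, and adds two mediation models. It contains no count of reactions, stops or individual worsening.

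**The concern.** Section 4.2 does more than stay silent on safety. It gives a reason for setting no safety endpoint, and other sections of the same document contradict that reason. Minimal risk is not the same as no risk, and the omission is made to rest on the second.

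The omission matters because the protocol itself describes the two arms differently: strong reactions are thought possible with TIP, while HET content is not expected to cause distress. Participants are selected for past tonic immobility and elevated PTSD symptoms (section 10.2). A randomized comparison is the natural place to see whether reactions differ by arm. As planned, the trial would report mean change and nothing on how many people reacted badly in the session, stopped because of distress, or deteriorated.

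**Working it through.** **Plan's own figure.** There is none to reproduce. No number in the protocol depends on this point, and the total of 120 comes without a derivation.

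**Step 1: the text, side by side.**

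| Question | Section 4.2 | Elsewhere in the protocol |
|---|---|---|
| Is any risk foreseen? | None | 15.1: distress during tasks; strong reactions to TIP |
| Is a response provided? | Not addressed | 6.3 and 15.1: therapist and on-call supervisor |
| Is the response recorded? | Not addressed | No section describes a log of call-ins or of reasons for stopping |
| Is harm tabulated by arm? | No endpoint | 17.1: not included |

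The N/A in section 18.0 follows from the minimal-risk classification and explains why there is no safety monitoring. It does not make the reason in 4.2 true.

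**Step 2: what the planned models would and would not show.** Guilt and shame are modelled at pre-intervention, post-intervention, week 1 and month 1, and PTSD symptoms at pre-intervention, week 1 and month 1. A mean shift in the wrong direction would be visible. A minority who worsen can be hidden behind a mean benefit, and an acute reaction in the session need not appear in any of these scores.

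**Step 3: what a count could tell.** Inputs: total 120 (section 6.2). The allocation ratio is not stated in 6.1, so n = 60 per arm is assumed, with 50 to 70 as the range. The protocol gives no event rate, so 1%, 2% and 5% are assumed.

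Upper one-sided 95% limit with zero events, 1 − 0.05^(1/n):
- n = 60: 1 − 0.05^(1/60) = 4.9%
- n = 50: 5.8%
- n = 70: 4.2%

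A two-sided exact 95% interval, with upper limit 1 − 0.025^(1/n), would reach 6.0% at n = 60.

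Chance of at least one event in an arm, 1 − (1 − p)^n:

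| True rate p | n = 50 | n = 60 | n = 70 |
|---|---|---|---|
| 1% | 39.5% | 45.3% | 50.5% |
| 2% | 63.6% | 70.2% | 75.7% |
| 5% | 92.3% | 95.4% | 97.2% |

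**Step 4: could it be a test?** Normal approximation, two-sided 5%, 60 per arm: power = Φ[(|p1 − p2| − 1.96·√(2p̄(1 − p̄)/n)) / √(p1(1 − p1)/n + p2(1 − p2)/n)], where p̄ is the mean of p1 and p2.
- 5% vs 1%: (0.04 − 1.96 × 0.0311)/0.0309 = −0.68, so power is about 25%.
- 10% vs 2%: (0.08 − 1.96 × 0.0434)/0.0427 = −0.12, so power is about 45%.

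Counts by arm are informative as description. They would not support a powered safety comparison.

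**The case against.** The best defence is that 4.2 is loosely worded. The sentence before the quoted one classifies the study as minimal risk, 15.1 says the same, and 18.0 is consistent with it. On that reading 4.2 means no risk beyond minimal, and a wording correction is enough. This is a fair account of what was probably intended. It still leaves the decision on endpoints resting on a statement that the document contradicts, and nothing by arm on acute reactions or individual deterioration.

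Four stronger readings are tempting, and the documents do not support them.

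- *Safety endpoints were dropped.* Nothing shows that any were planned and removed. Section 4.2 declares none.
- *Harm would go wholly unmeasured.* Mean worsening in guilt, shame or PCL-5 would show in the 17.1 models.
- *Any harm must differ by arm.* Both arms complete the questionnaires, for which 15.1 allows distress. The modified shame and guilt scale in 6.5 directs attention to the immobility experience with no restriction by arm. A higher risk with TIP is plausible on the protocol's wording, but not established.
- *The data will exist anyway.* This holds for the PCL-5. No section says that call-ins or reasons for withdrawal are recorded, so these need a log.

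The defence is also right that counting every PCL-5 increase would be a poor harm measure. With no true change and symmetric measurement error, nearly half of participants would score higher by chance. Selection on elevated scores would push the count down in both arms through regression to the mean. A margin is needed, and the count should be read against HET.

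**Conclusion.** The point holds in a limited form. The protocol's stated reason for having no safety endpoint conflicts with its own account of foreseeable reactions. Followed as written, the trial would give no account by arm of acute reactions, distress-related stops or individual worsening. No planned efficacy estimate or test is affected.

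The size of the gap can only be illustrated, because both the equal split and the event rates are assumptions. Even a clean TIP arm of 60 would leave true rates up to 4.9% open (4.2% to 5.8% over the assumed range of arm sizes), so the trial could not show an absence of risk. If reactions are not very rare, at least one is likely to occur and would have no place in the planned reporting.

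Section 14.1 adds a reason to record why people stop. It names non-completion of TIP but not of HET as a possible ground for removal, so a person who stops TIP because of distress might be removed without the reason being visible. Whether this would happen cannot be told from the document.

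**What to change.** 1. Reconcile sections 4.2, 6.3 and 15.1. For example, 4.2 could say that risk is minimal and as described in 15.1.
2. In both arms, log each therapist call-in under 6.3 and the reason for any stop or withdrawal.
3. In 17.1, add one descriptive table by arm with exact 95% intervals, giving call-ins, distress-related stops, and participants whose PCL-5 rose from pre-intervention to week 1 and to month 1 by more than a margin fixed in advance. The margin should exceed measurement error. The protocol gives no figure for it, so the investigators should state and justify one before the data are analysed.
4. State that the table is read against HET and is not a powered test.

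The cost is a short log, one extra table and a few sentences of protocol text. The PCL-5 scores are already planned. The report may look slightly less favourable. No change to participant care is proposed.

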**5.0 Study Intervention/Investigational Agent**

*5.1 Tonic Immobility Psychoeducation (TIP; Active Condition)*

TIP is a 45-minute computerized psychoeducation intervention aimed at addressing maladaptive cognitions and emotions associated with TI while using educational and behavioral techniques commonly used in the treatment of trauma-related disorders. Throughout the psychoeducation program vignettes will be presented to clarify concepts and promote participant engagement. In addition, practice exercises and rating scales will be integrated, where applicable, to increase the interactive nature of the program. The following modules will be addressed in the TI psychoeducation intervention: education, myth busting, and behavioral experiments.

*Health Education Training (HET; Control Condition)*

The Healthy Education Training intervention was developed as a 30-minute online intervention that provides education about physical health habits that can impact mental health, such as diet, exercise, and sleep. This intervention has been used in prior clinical trials to control for effects of general education, general coping techniques, and use of technology. Participants in past clinical trials have reported that HET is engaging and beneficial.

**6.0 Procedures Involved\***

- 6.1 The study adheres to a randomized controlled trial (RCT) design. Participants will be randomized to either the TIP or HET condition. Randomization will be stratified based on undergraduate vs. community member status. For each group, a random number table will be generated in Excel with either 1 = TIP or 2 = HET assigned to each participant ID. After completion of consent, the participant will receive their ID (assigned in sequential order) and the research assistant will prepare the corresponding treatment.

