## PROTOCOL TITLE: Development and Evaluation of a Tonic Immobility Focused Psychoeducational Intervention - RCT

6.2 The study proposes to enroll 120 participants to test the efficacy of the TIP intervention, compared to a HET control condition. All data collection will be conducted using Qualtrics. The study will be comprised of a total of three time points: Baseline, Week 1 follow-up, and Month 1 follow-up.

First, eligible participants will read and sign an informed consent that outlines all study procedures, details limits to confidentiality, and emphasizes that participants may discontinue participation at any time with no penalty.

The first appointment, baseline, will include pre-intervention self-report measures, the completion of one of the two interventions (TIP or PHET), and post-intervention self-report measures. The baseline appointment is expected to take 90 minutes. Participants will be compensated with a \$30 gift card or 1.5 course credits. All baseline procedures will be conducted either in-person within the Anxiety and Behavioral Health Clinic research suite or virtually via HIPAA-compliant Zoom. For in-person sessions, all COVID-19 related federal, state, and local guidelines as well as FSU IRB regulations will be followed. See section 6.3 for further information on COVID-19 safeguards.

The second and third appointments, week 1 and month 1 follow-up, will be completed online. Participants will be contacted via email and asked to complete a battery of self-report measures via a Qualtrics survey link. The questionnaire is expected to last 30 minutes and participants will be compensated either a \$10 gift card or 0.5 course credits for the completion of each appointment.

After the completion of the month 1 follow-up appointment, participants will be debriefed and individuals in the control condition will be given the opportunity to receive the active treatment condition.

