## 12.0 Local Number of Subjects

*12.1 Indicate the total number of subjects to be accrued locally.*

120 participants will be enrolled from Florida State University and the Tallahassee, FL area.

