**17.0 Data Management\* and Confidentiality**

**17.1** *Describe the data analysis plan, including any statistical procedures or power analysis.*

Preliminary analyses and data screening will be conducted prior to the primary analyses. This will include checking equivalence of random assignment to treatment condition based on key baseline characteristics. Specifically, analyses will be conducted to ensure that there are not baseline differences between condition (active vs. control) in terms of age, gender, and TIQ total scores.

Hierarchical linear regression analyses will be conducted to examine the impact of intervention condition on early treatment outcomes including posttreatment guilt, posttreatment shame, and week 1 PTSD symptoms. Analyses will be conducted in SPSS version 27.0.

Latent difference score analyses will be utilized to examine the differential change in guilt, shame, and PTSD symptoms between intervention conditions, across all study timepoints. Analyses will be conducted in Mplus version 8.0 (Muthén & Muthén, 1998-2017). Full information maximum likelihood (FIML) with the adjusted Yuan-Bentler scaled chi-square index (Y-B  $\chi^2$ ) will be utilized when possible in order to account for missing data. To determine model fit, the S-B  $\chi^2$  statistic as well as several indices will be used.

Three separate models will be estimated for the impact of treatment condition on guilt, shame, and PTSD symptoms. The effects of treatment condition on changes in guilt from pre-intervention to post-intervention (change 1), from post-intervention to week 1 (change 2), and from week 1 to month 1 (change 3) will be examined using a multi-group latent difference score (LDS) approach (Mun et al., 2009). The same methods will be used to examine effects of treatment condition on shame from pre-intervention to post-intervention (change 1), from post-intervention to week 1 (change 2), and from week 1 to month 1 (change 3) and PTSD symptoms from pre-intervention to week 1 (change 1), and from week 1 to month 1 (change 2).

The indirect effects of treatment condition on PCL-5 scores at month 1 through week 1 guilt and shame will be examined in two separate

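### Section 6.1 stratifies by undergraduate versus community status but states no blocks or ratio within strata, so the stratification as written has no balancing effect

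*Combined protocol and SAP*

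**What the plan says.** Section 6.1 describes a two-arm trial and names one stratification factor: "Randomization will be stratified based on undergraduate vs. community member status". For each of the two groups, "a random number table will be generated in Excel with either 1 = TIP or 2 = HET assigned to each participant ID". After consent, "the participant will receive their ID (assigned in sequential order) and the research assistant will prepare the corresponding treatment". Neither 6.1 nor any other section gives an allocation ratio, a block size, a permutation scheme or a fixed number per arm.

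The total is 120 (section 6.2: "The study proposes to enroll 120 participants to test the efficacy of the TIP intervention"). Section 12.1 repeats it without dividing it between students and community members.

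In section 17.1 the preliminary analyses include "checking equivalence of random assignment to treatment condition based on key baseline characteristics", specified as "baseline differences between condition (active vs. control) in terms of age, gender, and TIQ total scores". Recruitment group is not on that list, and none of the models described in 17.1 names it as a term.

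**The concern.** Stratifying the list helps only if the draw is restricted inside each stratum, for instance by permuted blocks. If every ID gets an independent 1 or 2, keeping two tables instead of one changes nothing about how the arms fill up. Section 6.1 therefore names a design feature and then describes a procedure that does not deliver it.

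The sponsor chose this factor, and the documents show that the two groups differ in recruitment and screening route (sections 10.1 and 13.3) and in compensation, course credit against gift cards (section 13.5). At stake is a chance difference between arms in the mix of students and community members. With the stratum absent from the stated baseline check and models, the plan has no stated step that reports such a difference or adjusts for it.

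**Working it through.** **Inputs.** From the documents: N = 120 (6.2, 12.1); two strata (6.1); 1 or 2 assigned per ID from one table per stratum (6.1). Assumed, because not stated: probability 1/2 for each arm; independent draws; community stratum s = 20, 30, 40 or 60 of 120. The documents give no figure for arm balance, so there is none to reproduce.

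**Step 1: two tables against one.** Under independent draws the number of TIP allocations in a stratum of size n is Binomial(n, 1/2), independent of the other stratum. That holds whether the draws come from one table or two. The joint distribution of arm-by-stratum counts is the same, so the separate tables add no balance.

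**Step 2: arm sizes overall (n = 120).** The SD of the difference in arm sizes is √120 = 10.95. The exact chance of 60:60 is C(120,60)/2^120 = 0.073. The chance of 70:50 or worse, either way, is 2·P(X ≥ 70) = 0.082. The central 95% range runs from 49:71 to 71:49.

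**Step 3: within one stratum.** For n = 30, the chance of 20:10 or worse is 2·P(X ≥ 20) = 0.099.

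**Step 4: community share between arms.** Let a ~ Bin(s, 1/2) and b ~ Bin(120 − s, 1/2) be the community and student counts in TIP. The difference in share is |a/(a+b) − (s−a)/(120−a−b)|. Summing exactly over all (a, b), with ties at exactly 10 points counted:

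| Community members (assumed) | P(difference ≥ 10 points) |
|---|---|
| 20 | 0.154 |
| 30 | 0.226 |
| 40 | 0.273 |
| 60 | 0.315 |

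A difference of 20 points or more has probability 0.3% (s = 20) to 3.5% (s = 60) by the same sum.

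**Step 5: cost in power.** Relative efficiency at 49:71 is 4·49·71/120² = 0.966. Assume a standardised effect of 0.5 and two-sided 0.05, for illustration only, with power = Φ(0.5/√(1/n₁ + 1/n₂) − 1.96):
- 60:60 gives Φ(2.739 − 1.96) = 78.2%
- 49:71 gives Φ(2.692 − 1.96) = 76.8%

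The loss is 1.4 points.

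**Step 6: shift in the estimate.** If the strata differed by 0.5 SD on an outcome (assumed), a 10-point difference in share would move an unadjusted contrast by 0.10 × 0.5 = 0.05 SD. The standard error at 60:60 is √(1/60 + 1/60) = 0.18 SD.

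**Step 7: after restriction.** With blocks of 4 and 6, only the last, incomplete block in a stratum can be unbalanced. The arm difference is then at most 3 per stratum and 6 overall. For arm differences d₁ (community) and d₂ (student), with D = d₁ + d₂, the share difference is 2[d₁(120 − s) − s·d₂]/(120² − D²). The largest value is at d₁ = 3, d₂ = −3: 2·3·120/120² = 0.05. Differences of 10 points can no longer occur.

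**The case against.** The absence of blocks is read from silence. Section 6.1 never says the draw is simple or unrestricted, and an equal list of 1s and 2s sorted by a random number in Excel could be described in the same sentence. This stands. The finding is about what the text specifies, not about what the team did. A reader who follows 6.1 literally would still produce an unrestricted list.

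Unrestricted randomisation at this size is also legitimate. The arms are equal in expectation, the allocation is unbiased, and chance imbalance is already covered by the standard error. Step 6 shows that a 10-point difference in mix moves the estimate by well under one standard error under the assumed stratum effect. This stands too, and it limits the seriousness.

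A reader might infer that an imbalance in recruitment group would go unnoticed. The documents do not support that. With one table per group, arm counts by stratum can be read from the lists; the demographic survey in 6.5 records educational and occupational level; and the age check in 17.1 may partly track student status. What holds is that the stratum is not named in the check or the models.

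Finally, blocks cost something. The research assistant prepares each assigned treatment and so sees past allocations, which makes the end of a block partly guessable. Blocks of 2 would be the worst in this respect.

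**Conclusion.** The point holds for the text of 6.1: stratification is stated, no restriction within strata is given, and without one the stratification has no balancing effect. The consequence is moderate to small. A 10-point difference in community share has a chance of about 15% to 32%, depending on the unstated split, and 70:50 or worse overall has a chance of 0.08. The power cost is about 1 to 2 points at 49:71. These figures rest on independent draws at probability 1/2, stratum sizes of 20 to 60 community members and, for power, an assumed effect of 0.5.

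A reader might go further and conclude that the randomisation is biased or the comparison invalid. The documents do not support this: as described, the allocation is random, and what is missing is enforced balance. Nor do they establish that blocks were deliberately left out.

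**What to change.** In 6.1, specify a 1:1 permuted-block list for each stratum, with randomly varying block sizes (for example 4 and 6, avoiding 2) that are not disclosed to session staff. If a restricted list was already intended, state its ratio and form instead. Naming recruitment group in the 17.1 baseline check and as a model covariate would be a useful complement, but it does not replace the change in 6.1.

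The cost is one sentence in 6.1 and, if the list is unrestricted, regenerating it before enrolment, which Excel can do by shuffling within blocks. The small downside is some added predictability, since the research assistant sees past allocations. Varying, undisclosed block sizes limit it.
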